Protocol

Randomized Clinical Trial of Intraoperative ECMO versus Cardiopulmonary Bypass in Lung Transplantation

Amendment 1. September 27, 2017

TABLE OF CONTENTS

DEFINITIONS, ACRONYMS, AND ABBREVIATIONS.

ABSTRACT.

BACKGROUND AND SIGNIFICANCE

ENDPOINTS.

STUDY DESIGN.

STUDY POPULATION.

DEFINITIONS AND MEASUREMENT OF ENDPOINTS.

CLINICAL CENTERS.

DATA COLLECTION.

DATA MANAGEMENT

ANALYTIC PLAN.

REFERENCES.

DEFINITIONS, ACRONYMS, AND ABBREVIATIONS

CPB Cardiopulmonary bypass

ECMO Extracorporeal membrane oxygenation

PGD Primary Graft Dysfunction

STUDY INVESTIGATOR

PI: [name]

Co-Authors

[name]

[name]

[name]

[name]

[name]

[name]

[name]

[name]

ABSTRACT

Title	Randomized Clinical Trial of Intraoperative ECMO vs. Cardiopulmonary Bypass in Lung Transplantation
Background	Cardiopulmonary bypass (CPB) is the current standard of care for intraoperative cardiorespiratory support during lung transplantation. However, the blood-air interface and the need for full systemic anticoagulation may lead to systemic inflammatory response and coagulopathy. Some reports have suggested that intraoperative support with extracorporeal membrane oxygenation (ECMO) in lieu of CPB may be a better alternative with decreased bleeding, blood requirements and rates of primary graft dysfunction (PGD).
Hypothesis	patients on ECMO will have 
• decreased transfusion requirements,• decreased intubation time,• lesser PGD grade at 72 hours• No increase in major adverse events• Pump duration may be longer.
Study Design	A prospective randomized trial comparing intraoperative support with ECMO and CPB. This will be a superiority trial for efficacy and non-inferiority for safety. The allocation ratio will be 1:1.
Number of Participants	40 in each arm
Study Objectives	Determine if ECMO compared to CPB during lung transplantation has a beneficial effect on

	short term outcomes after lung transplantation.
Interventions	When patient need intraoperative cardiopulmonary support, patient would be randomized to ECMO or CPB
Inclusion Criteria	All patients undergoing lung transplantation. Not all patients randomized will need intraoperative support

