Currently, many centers would use one technique or the other and both are considered current standard of care and best practice. At Cleveland Clinic, we have used both methods. The method of support is currently not discussed with patients as both are considered acceptable.

HYPOTHESIS

Our hypothesis is that patients on ECMO will have a decreased transfusion requirements, decreased intubation time, lesser PGD grade at 72 hours without increase in adverse risk. Pump duration may be longer.

ENDPOINTS

Primary

- 1 Bleeding: total PRBC transfusion requirements at 72hours

Secondary

Superiority

1. Ventilation time (days)
2. Intraoperative PRBC transfusion rates
3. Duration of support
4. Primary graft dysfunction (PGD) grade at 72 hours.
5. Transfusion requirement of FFP, platelets, cryoprecipitate at 72 hours.

Non-inferiority:

1. Composite outcome of: 30-day or discharge date (if earlier than 30 days) mortality, bleeding requiring reoperation, new ECMO, new renal failure requiring dialysis

STUDY DESIGN

Randomized clinical trial with an allocation ratio of 1:1, comparing CBP versus ECMO for intraoperative cardiopulmonary support. Study will have a superiority design for efficacy and a non-inferiority design for safety.

Randomization:

All lung transplant patients will be consented preoperatively. Patients will be randomized at the beginning of the case and the configuration of the cardiopulmonary bypass machine will be set accordingly. Not all patients randomized will require intraoperative cardiopulmonary support.

Circuit design:

separate tubing that connects the venous return line directly to the pump head bypassing the venous reservoir. The venous reservoir is still connected and but clamped.

Incision and cannulation:

The type of incision will be at the discretion of the surgeon but can be sternotomy, thoracotomy or clamshell. If patient has a sternotomy and randomized to ECMO, venous cannula should be placed through a percutaneous femoral venous cannula to avoid the potential of air embolus.

Anticoagulation:

ACT target 200-250. Repeat every 30 min. Bolus 5000U, give supplemental doses as needed.

Conversion to full cardiopulmonary bypass:

Give full dose heparin; release the clamp on the venous reservoir after act is above 480.

Reasons to convert from ECMO to CPB intraoperatively:

- Significant bleeding to allow blood to return back to circuit

- Heart remain too distended to allow mobilization

- Air in the circuit

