- The need to fibrillate or arrest the heart

- Hemodynamic instability from positioning

Other safety mechanisms:

- Consider system for rapid transfusion

- Double lumen intubation: the heart does not decompress and there's ejection requiring the need for ventilation.

- Use an urchin or heartnet for heart positioning if necessary

- Once the patient is decannulated, the blood from the circuit can be re-transfused back into the patient

Transfusion triggers:

Transfusion triggers will be hematocrit of .24 and at the discretion of the staff surgeon, anesthesiologist or intensivist. Coagulopathy will be corrected based on Cleveland clinic post cardiectomy bypass protocol (appendix 2) and at the discretion of surgeon, anesthesiologist or intensivist.

Patients will be extubated at the discretion of the staff surgeon and intensivist.

Patients who are consented but not included in the study and patients who are felt to be better candidates for cpb will be followed in a separate registry

NUMBER OF PARTICIPANTS

40 Patients in each arm

Power calculation (based on 2015 CCF outcomes)

- Safety

 - 30 day mortality: 6.2%

Bleeding requiring reoperation: 10.3%
New ECMO: 1.3%
New renal failure requiring dialysis: 10.3%
Composite outcome 18.6%.

Sample size calculation
Non-inferior margin: 5%
90%: 283, 80%:205, 70%: 155
Non-inferior margin: 10%
90%: 77, 80%:56, 70%: 42

Efficacy

PGD grade at 72 h:

0:	24.4%
1:	47.4%
2:	14.1%
3:	14.1%

RBC transfusion

CPB: 14.7(8.4) vs ECMO 9.3(6.9)
90%: 51, 80%:39, 70%: 30

Ventilation time

CPB: 16.5days (27.3) vs ECMO 8.25 (16.4)
90%: 83, 80%:62, 70%: 49

For literature outcomes, see appendix 1.

STUDY POPULATION

The study population will be all patients undergoing lung transplantation at our institution. These patients will be randomized using the block method and allocated to either the CPB or ECMO group. Not all patients randomized will require intraoperative support.

Inclusion Criteria

All consented patients undergoing lung transplantation.

Exclusion Criteria

Patients undergoing concomitant cardiac operations with indication for obligate use of cardiopulmonary bypass

Patient with specific anatomy that require full cardiac decompression such as severe pulmonary hypertension or large heart that are shifted severely into the left chest (relative)

Patients with high likelihood of significant pleural bleeding that will require returning the blood back into the cardiotomy reservoir (relative)

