Patients bridged to transplant with ECMO

Cystic fibrosis/bronchiectasis/resistant infection patients where surgeon will need to remove both lungs prior to implantation

Patients who the surgeon feels would be better served with CPB rather than ECMO
These patients will be entered into a registry and followed.

CLINICAL CENTERS

Patient Confidentiality

All patient records will be kept confidential according to HIPAA guidelines. Study investigators and site Institutional Review Boards (IRBs) may review source documentation as necessary, but will then transmit this information to Clinical Investigations at Cleveland Clinic according to the patient's unique study number. Linkage of that study number to the actual patient will reside only at the individual institutions. Aggregate data from this study may be published as per publication policy documented in the trial agreements; no data with patient identifiers will be published.

Consent

Patients will be consented for surgery ahead of time at time of listing

DATA COLLECTION

Data will be collected from Epic Systems chart review and supplemental data collection. All necessary data are currently already collected. Study terminates at patient discharge. No additional testing or followup is needed beyond what is already done for this patient population.

DATA MANAGEMENT

The data will be stored in Red Cap Sheets strictly secured and managed by the lead and other co-investigators. No identifiable information will be shared with outside parties, ensuring that all data will remain safely stored on Cleveland Clinic Main Campus user hard drives and will only be shared amongst our study team.

ANALYTIC PLAN

Basic statistical analysis will be required to compare the outcomes in the groups. Patients who are excluded will be included in a separate registry.

Analysis will be based on intention to treat.

A statistical significant difference is defined as a two-sided P value less than 0.05.

REFERENCES

1. Machuca (2015) Outcomes of intraoperative extracorporeal membrane oxygenation versus cardiopulmonary bypass for lung transplantation.
2. Bermudez (2014) Outcomes of Intraoperative Venoarterial Extracorporeal Membrane Oxygenation Versus Cardiopulmonary Bypass During Lung Transplantation.
3. Ius (2012) Lung transplantation on cardiopulmonary support: Venoarterial extracorporeal membrane oxygenation outperformed cardiopulmonary bypass.

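### Safety is designed as a non-inferiority comparison, but the plan adopts neither of its two listed margins and gives no non-inferiority rule

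*Combined protocol and SAP*

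**What the plan says.** - **Design.** The Abstract states: "This will be a superiority trial for efficacy and non-inferiority for safety". The Study Design section repeats it: "Study will have a superiority design for efficacy and a non-inferiority design for safety". The Endpoints section places one item under non-inferiority: a composite of death (to 30 days, or to discharge if earlier), reoperation for bleeding, new ECMO and new dialysis.
- **Margins.** Number of Participants, under the heading "Power calculation (based on 2015 CCF outcomes"), gives "Composite outcome 18.6" (percent) as the composite rate. It then prints "Non-inferior margin: 5" (percent) with sizes 283, 205 and 155 for 90%, 80% and 70% power, and "Non-inferior margin: 10" (percent) with "90%: 77, 80%:56, 70%: 42". Neither margin is named as the trial's margin or justified. The scale (absolute or relative) is not given, nor whether the sizes are per arm or total.
- **Analysis.** The Analytic Plan calls for basic statistical comparison of the groups, by intention to treat, and ends with "A statistical significant difference is defined as a two-sided P value less than 0.05". It contains no non-inferiority hypothesis, margin, confidence limit or test, and no other section supplies one.

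**The concern.** Non-inferiority is shown by excluding a stated excess of harm: a confidence limit must lie on the right side of a margin fixed in advance. Here both parts are missing. A two-sided test for a difference asks another question, and neither of its outcomes shows that ECMO is non-inferior within a margin.

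The rule and the margin would therefore have to be supplied later, possibly with the results in view. Because two margins are already printed, either could be cited afterwards as the planned one. At stake is the part of the hypothesis that says ECMO brings its benefits without added adverse risk.

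**Working it through.** **Inputs.** From Number of Participants: 40 per arm; composite rate 18.6%; margins 5% and 10%; RBC means (SD) 14.7 (8.4) and 9.3 (6.9). From the Analytic Plan: two-sided 0.05. Assumptions: the margins are absolute percentage points, and 18.6%, a 2015 institutional rate not labelled as a CPB rate, applies to the CPB arm. CPB rates of 10% and 30% were also examined.

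**1. Does the sample size reveal the margin?** The RBC entry gives n = 2·SD²·(z₀.₉₇₅ + z₀.₈₀)²/difference² = 2·8.4²·(1.960 + 0.842)²/5.4² = 38.0 per arm, or 39 with a t-based calculation. The plan prints 39, so that list is per arm, and 40 fits it. If the non-inferiority sizes are also per arm, 40 is below all six (the smallest is 42). If they are totals, the planned 80 exceeds 77 (10% margin, 90% power) and is below 155. That would point towards 10%, but no text adopts it.

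The printed non-inferiority sizes do not help to decide. With 18.6% in both arms, one-sided 0.05 and 80% power, n = 2·0.186·0.814·(1.645 + 0.842)²/M² gives 188 per arm for M = 0.10 and 749 for M = 0.05, against 56 and 205 printed. That mismatch is a separate matter, and this point does not rest on it.

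**2. Can the margin decide the verdict?** Take the natural rule: non-inferior if the upper 95% Newcombe limit for ECMO minus CPB is below M. With Wilson limits l and u for each arm,

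U = (pE − pC) + √[(uE − pE)² + (pC − lC)²].

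For 4/40 ECMO against 7/40 CPB: pE = 0.100, uE = 0.2305, pC = 0.175, lC = 0.0875. So U = −0.075 + √(0.1305² + 0.0875²) = −0.075 + 0.157 = +0.082. This passes at 10 points and fails at 5. With CPB still at 7/40, the limits for ECMO counts of 2, 3, 4, 5 and 7 are +2.0, +5.1, +8.2, +11.2 and +16.9 points, so the verdicts split only at 3/40 and 4/40.

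**3. How often?** Summing binomial probabilities over all outcomes at 40 per arm:

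| CPB rate | ECMO rate | Passes at 10 points | Passes at 5 points | Verdicts differ |
|---|---|---|---|---|
| 18.6% | 18.6% | 21% | 8% | 13% |
| 18.6% | 13.6% | 44% | 22% | 22% |
| 18.6% | 9.3% | 69% | 43% | 26% |

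Across the scenarios examined, verdicts differ in 10% (CPB 30%, equal rates) to 28% (CPB 10%, ECMO rate halved). When the true excess equals the margin and CPB is 18.6%, the rule passes in 2.8% of trials (10 points) and 2.6% (5 points), close to the nominal 2.5%.

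**4. Secondary check: the difference test standing in for a rule.** If P ≥ 0.05 were read as safety, a true 10-point ECMO excess over 18.6% would be non-significant in 87% of trials by Fisher's test (84% to 90% for CPB rates of 10% to 30%) and in 82% by chi-square (75% to 85%). For example, 11/40 ECMO against 7/40 CPB gives P = 0.28 by chi-square, yet the Newcombe upper limit is +27.7 points, beyond both margins.

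**The case against.** The strongest reply is that this is terseness with little consequence. A two-sided 0.05 level corresponds to a 95% interval, and the protocol confines the margin to two values. In the base-case scenarios those values agree in 74% to 87% of trials. With equal rates even the 10-point rule passes only 21% of the time, so sample size limits the safety answer more than the missing sentence does. The endpoint is also secondary. All of this is fair and limits the size of the point. It does not supply a margin or a rule, and disagreement in 10% to 28% of trials is too much to leave to a later choice.

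Two stronger readings are tempting, and the documents support neither. A reader might infer that the trial will treat P>0.05 as proof of safety. The Analytic Plan only defines a significant difference; it never assigns that test to the composite or says how a non-significant result will be read. The 87% and 82% figures therefore measure a hazard, not a stated intention. A reader might also infer that 40 per arm falls short of every printed non-inferiority size. That holds only if those sizes are per arm, which is likelier given the RBC entry but is not stated.

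**Conclusion.** The point holds. A non-inferiority design is declared, two margins are listed with neither adopted, and no rule exists by which the composite could be declared non-inferior. Neither reading of the sample size settles the margin.

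The absence of a rule is plain from the text and needs no assumption. The size of the consequence rests on absolute margins, 40 analysed per arm, a Newcombe interval and the assumed event rates. Lower ECMO rates are plausible but not certain. In Appendix 1, one observational series has dialysis at 8% with ECMO against 22% with CPB, but postoperative ECMO at 18% against 15%; another has new postoperative ECMO at 4% against 26%.

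This should be corrected, but it does not touch the primary PRBC comparison.

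**What to change.** Add to the Analytic Plan:

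> The safety composite is declared non-inferior only if the upper limit of the two-sided 95% Newcombe confidence interval for the ECMO minus CPB risk difference, in the intention-to-treat set, is below M percentage points. Otherwise the result is inconclusive; P>0.05 is not evidence of safety.

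The sponsor should fix and justify one absolute M, and keep the one named interval method, before outcomes are compared by arm.

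Add a supportive analysis in patients who received their allocated support. Some randomised patients will need no support, and the protocol foresees conversion from ECMO to CPB; both can pull the arms together and so favour non-inferiority. This analysis should stay supportive, because it drops patients for reasons that arise after randomisation.

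State the rule's power at 40 per arm. With 18.6% in both arms it is about 21% at a 10-point margin and 8% at 5 points.

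Alternatively, drop the non-inferiority label and report the composite descriptively with its 95% interval.

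**Cost.** A few sentences and one extra analysis; no further outcome data, and the two-sided 0.05 level and intention to treat remain. The downside is that the safety claim will often be inconclusive at this sample size, and the plan would have to say so.

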Appendix 2:

Post Cardiopulmonary Bypass Coagulopathy Protocol

CCF TEG Normal Values:

R time: 2-8 mins

K time: 1-3 mins

Angle: 55-78 degrees

MA: 51-69

EPL 0-15%

LY30 0-8

Once the bladder temperature reaches 36.5° C during rewarming on cardiopulmonary bypass, obtain the following labs: TEG with heparinase, PT, INR, fibrinogen and platelet count.

1. If the R time and INR is elevated, consider transfusing FFP as below. If the R time is normal, but the INR is elevated and there is microvascular bleeding once the temperature has normalized, transfusion of FFP can still be considered.

a. $8 < R < 11$ (mins) → 1 U FFP

b. $11 < R < 14$ (mins) → 2 U FFP

c. $14 \leq R$ (mins) → 4 U FFP

2. If the α angle and fibrinogen is decreased, consider transfusing cryoprecipitate as below. If the α angle is normal, but the fibrinogen is still decreased and there is microvascular bleeding once the temperature has normalized, transfusion of cryoprecipitate can still be considered.

a. Angle $< 45^\circ$ → 10 U cryoprecipitate

3. If the Max Amplitude (MA) and platelet count is decreased, consider transfusing platelets as below. If the MA is normal, but the platelet count is decreased and there is microvascular bleeding once the temperature has normalized, transfusion of platelets can still be considered.

a. $46 \leq MA < 51$ (mm) → 1 U Platelets

b. $40 \leq MA < 46$ (mm) → 2 U Platelets

c. $MA < 40$ (mm) → 2-3 U Platelets

4. If the LY30 is elevated at greater than 8%, consider the addition of antifibrinolytic therapy with aminocaproic acid infusion
